10.2 Sample Size

This is a non-inferiority trial designed to determine whether the overall survival rate for SBRT is clinically (and statistically significantly) no worse than the overall survival for SR. We used published survival rates from the literature for SR in this patient population [2, 8, 19, 103]. The 3-year survival rate for SR (control group) appears to be approximately 80%. We will deem SBRT as non-inferior to SR if the 3 year overall survival rate for SBRT is no more than 0.10 less than that for SR. In other words, if the survival rate for SBRT at 3 years is more than 0.10 less than that for SR. In other words, if the survival rate for SBRT at 3 years is more than 0.10 less than the 3 year survival rate for SR, we will declare SBRT to be an inferior treatment compared to SR in terms of overall survival. To power the study, we assumed an exponential distribution for the survival rate and a HR of 1.60 (which reflects a 10% 3-year survival rate for SR is at least 0.10 greater than that for SBRT (0.80 for SR versus 0.70, or less, for SBRT). The alternative hypothesis is that the HR is 1.00 or that the 3 year survival rate for SR compared to SBRT is no more than 0.10. If we reject the null hypothesis, we will assume the two treatments are equivalent with respect to overall survival, if we do not reject the null hypothesis, we will assume that SR is superior to SBRT is no more than 0.10.

To determine the sample size for the trial we assumed a significance level of 0.05, an HR of 1.60 (SBRT versus SR, for the null hypothesis) and set power to be 90%. We plan a single interim analysis when half of the expected events (deaths) have occurred; this will be for futility only. Assuming a 3-year survival rate of 0.80, a HR of 1.60 yields a 3-year survival rate for SBRT of 0.70 or less for the null hypothesis. Assuming an accrual rate of 10 patients per month, an expected accrual duration of 40 months (3 1/3 years), and a minimum follow-up of 42 months (3.5 years), the necessary sample size is 400 eligible patients (200 per arm). To ensure that there is an adequate number of eligible patients (including patient refusals after randomization and prior to treatment), we will have a target accrual that is approximately 5% greater than this or 420 patients. This trial is expected to accrue in approximately 40 months and the final analysis will occur after 166 deaths have been observed or about 82 months (6.8 years) after the first patient is enrolled.

In summary, a sample size of 200 eligible patients in each arm (target accrual is 420 including a 5% over accrual for patients who withdraw consent prior to treatment initiation) would mean that if the true hazard ratio is 1, then there is a 90% probability of declaring non-inferiority, and if the true hazard ratio is 1.6, there is a 5% probability of declaring non-inferiority.

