1.3 Objectives

1.3.1 Primary Objective

To ascertain whether patients treated by SBRT have a 3-year overall survival (OS) rate that is no more than 10% less than patients treated with SR.

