1.4.1 Accrual Goal

Target accrual for this study is 420 patients, with a projected accrual rate of 6-10 patients per month.

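### Section 10.2 times the trial at 10 patients per month, the top of the protocol's 6-10 range, and does not say whether 166 deaths or month 82 triggers the final analysis; under equal survival the two do not coincide at any rate in that range

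*Combined protocol and SAP*

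**What the plan says.** Section 1.4.1 (Accrual Goal): "Target accrual for this study is 420 patients, with a projected accrual rate of 6-10 patients per month".

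Section 10.2 (Sample Size) uses only the upper end: "Assuming an accrual rate of 10 patients per month, an expected accrual duration of 40 months". With that it takes 42 months of minimum follow-up and 400 eligible patients, raised to a target of 420. It repeats 40 months as the expected accrual period and adds that "the final analysis will occur after 166 deaths have been observed or about 82 months (6.8 years) after the first patient is enrolled". No figures are given for any other rate.

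Three other places bear on this:
- Section 10.3.2 puts the single futility look at 79 deaths and calls that half the information, which implies 158 deaths at the end, not 166.
- Section 10.1.1 promises at least 5 years of follow-up for overall survival. Sections 6 and 7 and the Study Calendar describe follow-up to 5 years.
- The primary objective (Section 1.3.1) is about a "3-year overall survival (OS) rate that is no more than 10% less than patients treated with SR".

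**The concern.** The sentence on the final analysis joins a death count and a date with 'or', as if they were one event. They can be one event only if deaths arrive at the assumed pace, and that pace rests on the most favourable accrual rate the protocol itself projects.

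If the date is followed, the analysis may have too few deaths to exclude HR 1.6 with the stated 90% probability when the arms are equal. It would also come before the stated minimum follow-up has been reached. If the death count is followed, power is protected, but the date on which the monitoring committee, the sites and the funder would plan is too early. The plan does not say which consequence it accepts.

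**Working it through.** **Inputs.** From Sections 10.2 and 10.3.2: SR 3-year survival 80%, exponential survival, margin HR 1.6, one-sided alpha 0.05, 1:1 allocation, 400 eligible patients, 420 target. The summary at the end of Section 10.2 defines power at true HR 1. From Section 1.4.1: 6-10 patients per month. My assumptions: uniform entry, no loss to follow-up (the plan gives no rate), and follow-up continuing until the analysis.

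**Formulas.**
- Monthly hazard: h = -ln(0.80)/36 = 0.00620.
- Expected deaths at month t, with N patients entering at rate r over A = N/r months: N × {1 − [exp(−h(t−A)) − exp(−ht)]/(hA)}.
- Power with d deaths: Φ(ln(1.6) × √d / 2 − 1.645).

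**The plan's own figure.** The Schoenfeld requirement is [2 × (1.645 + 1.282)/0.470]² = 155.1, so 156 deaths. Power is 90.5% at 158 deaths and 91.7% at 166. With the futility look at 79 deaths and the stated boundaries (0.031 and 1.63), it is 90.1% and 91.2%. The 90% therefore follows from either death count.

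**The pairing of 166 deaths with month 82.** At 10 per month with 400 patients, month 82 gives 127 deaths under HR 1 and 155 if deaths are counted at HR 1.6. The pairing is roughly consistent only in the HR 1.6 setting, not in the HR 1 setting where power is defined.

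**Accrual and follow-up for 420 patients.**

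| Rate per month | Accrual (months) | Last patient's follow-up at month 82 (months) |
|---|---|---|
| 10 | 420/10 = 42 | 40 |
| 8 | 420/8 = 52.5 | 29.5 |
| 6 | 420/6 = 70 | 12 |

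The 42-month minimum is met only for 400 patients at 10 per month. At 6 per month, (70 − 46)/70 = 34% of the 420 would have entered less than 36 months before month 82.

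**If month 82 is a cut-off (400 analysed).**

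| Rate per month | Deaths, HR 1 | Power | Deaths counted at HR 1.6 | Power with that count |
|---|---|---|---|---|
| 10 | 126.9 | 84.2% | 154.6 | 89.9% |
| 8 | 117.9 | 81.8% | 144.2 | 88.0% |
| 6 | 102.1 | 76.7% | 125.3 | 83.8% |

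Example at 6 per month: 0.470 × √102.1 / 2 − 1.645 = 0.73, and Φ(0.73) = 0.767. Accrual alone costs 84.2 − 76.7 = 7.5 points. The other 90 − 84.2 = 5.8 points are present at 10 per month.

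**If deaths govern: expected month of the target (420 to 400 patients).**

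| Rate per month | 166 deaths, HR 1 | 166 deaths, HR 1.6 | 158 deaths, HR 1 | 158 deaths, HR 1.6 |
|---|---|---|---|---|
| 10 | 103-107 | 85-88 | 98-102 | 81-84 |
| 8 | 108-112 | 91-93 | 103-107 | 87-89 |
| 6 | 117-121 | 100-102 | 112-116 | 96-98 |

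**If each patient's follow-up stopped at 60 months.** The most deaths expected under HR 1 are 400 × (1 − exp(−60h)) = 124, or 130 for 420 patients. Neither target would then be expected, whatever the accrual rate.

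**The case against.** The strongest reply is that the design is event-driven. Section 10.2 names the deaths first, the date is introduced with 'about' and equals 40 + 42, and Section 10.3.2 sets the interim by deaths. No section orders an analysis on a calendar date. On that reading slower accrual moves the date and leaves power intact. I accept this as the more natural reading. It does not rescue month 82 as a projection: under HR 1 the 166th death is expected at least 20 months later, even at 10 per month.

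A second reply is that 10 lies inside 6-10 and 400/10 = 40 is correct. That stands. This is an optimistic input with no sensitivity range, not a contradiction between sections.

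A third is that Section 10.4 provides twice-yearly review of accrual. It does, but such review cannot settle which half of the sentence governs.

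A fourth is that 158 deaths at 10 per month, counted at HR 1.6, do fall at about months 81-84. This probably explains the date. But it requires the SBRT arm to be at the margin, and Section 10.2 states 166.

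A reader might also infer that early censoring weakens the primary test in addition to the loss of deaths, or that every patient must reach 36 months. Section 10.3.1 does not support this. The test is a log-rank comparison with a confidence bound for the HR, so in this calculation censoring acts through the death count.

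**Conclusion.** The concern holds in limited form. The schedule uses the top of the protocol's own accrual range, the 42-month minimum follow-up is not met at month 82 for 420 patients at any rate in that range, and the two halves of the trigger do not coincide under HR 1 at 10, 8 or 6 per month. Either the date is followed and power falls below 90% (84%, 82% or 77%), or the deaths are followed and the date is late by about 20-39 months under HR 1, or 3-20 months if deaths are counted at HR 1.6.

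A reader might conclude that the trial has 77% power. The documents do not support that. The figure needs month 82 to be a calendar cut-off and accrual to run at 6 per month, and it includes a shortfall of about 6 points that slow accrual does not cause.

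The results rest on exponential survival at 80% over 3 years, uniform entry, no losses, and survival follow-up until the analysis. Losses would lower the death counts at a given date and push the dates later.

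**What to change.** In Section 10.2:

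1. Make the death target the only trigger for the final analysis. The 42 months of follow-up after the last patient that 10.2 already assumes may be added as a floor.
2. Use one death target throughout: 166, or the 158 implied by 79 as half the information. Align Section 10.3.2 with it.
3. Label month 82 as a projection, and replace it with accrual durations of 42, 52.5 and 70 months for 420 patients and the projected month of the chosen target at 10, 8 and 6 per month, stating the HR assumed.
4. State that survival follow-up continues beyond 5 years until the target is met, and align Sections 6 and 7 and the Study Calendar.

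The floor alone should not be printed as the analysis date. For 420 patients it falls at months 84, 94.5 and 112, when about 135, 144 and 157 deaths are expected under HR 1, all short of 166. A power column by accrual rate is not needed once deaths are the trigger.

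The cost is a few sentences, a small table and longer survival follow-up for the earliest patients. The stated final analysis moves about 20-39 months later under HR 1 with the 166 target. The number of patients, the margin and alpha do not change.

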6.2 Follow-up of Patients with Disease Relapse/Progression

Patients with local, regional or distant disease relapse/progression during or after protocol therapy will be followed for survival and quality of life, as required by the Study Calendar. Patients may be treated at the physician's discretion. NOTE: If resection is attempted after disease relapse/progression, submit operative and pathology reports and 4-week post-surgery adverse event data.

6.3 Follow-up of Patients Who Discontinue Treatment Early for Reasons Other Than Disease Relapse/Progression

Patients who discontinue protocol therapy for reasons other than disease relapse/progression will be followed as required by the Study Calendar.

7 Evaluation of Outcomes

All patients will be followed for 5 years for survival and disease relapse/progression. Adverse events including surgical morbidity and mortality and late radiation effects also will be monitored. Quality of life will be evaluated for patients who have consented to participate in that portion of the study.

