10.3 Planned Analyses

10.3.1 Primary Endpoint Analysis

The primary analysis will exclude patients who cancel (withdraw consent) prior to receiving treatment; we will tabulate the number (percent) of patients who withdraw prior to treatment and take actions if this percent appears to be greater than 5%. Patients who are randomized but received the opposite treatment to which they were randomized will be included in the analysis according to the treatment they received; it is expected

that the rate of patient crossover will be low. However, a sensitivity analysis using the fully intention to treat approach will also be performed. The primary endpoint will be analyzed using a one-sided log-rank test comparing the overall survival of the two arms and a one-sided (upper boundary) 95% confidence interval (CI) for the HR. If the 95% CI for the HR lies entirely below 1.6, this will be evidence that SBRT is non-inferior to SR. If the interval includes 1.6, this is evidence that SBRT is inferior to SR.

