10.3.2 Interim Analysis

While this trial is accruing, we will be closely monitoring Z4032 for the maturation of its results. The results of this trial are expected to be mature in 12/2011. If the analysis of Z4032 indicates that either SR alone or SR with brachytherapy is superior to the other, we will amend this trial to use the therapy found to be superior in Z4032 as the treatment in Arm 1 (the SR arm) of this trial. At this point, we would also amend the sample size based on the results of Z4032, if needed.

A single formal interim analyses for futility based on the primary endpoint will be conducted after 79 deaths have been observed. The rationale for performing a single interim analysis for futility is based on the following considerations: (1) there may be different time-related patterns of treatment-related mortality in the two arms, i.e., the hazards may not be proportional; (2) stopping early for non-inferiority before all patient have been randomized may be inappropriate given the potential importance of the adverse event profile and quality of life endpoints in deciding the preferred treatment; and (3) as a non-inferiority trial, early stopping for "success" (i.e. non-inferiority) is not ethically necessary and may undermine the general acceptance of the result. The interim analysis will take place after half the expected trial information (i.e. 79 deaths) has been observed.

Assuming a baseline rate of a three-year survival of 80% for the SR, a sample size of 400 provides 90% power to declare non-inferiority if the three-year survival rates are truly the same (i.e. HR = 1), using a one-sided logrank test with alpha = 0.05 for falsely declaring non-inferiority when the true three-year survival rate for the SBRT arm is 70%. The calculations are based on a two-sample survival non-inferiority calculation, performed using EAST version 4.0, with an 80% 3-year survival for the control arm, and a 10% non-inferiority margin. A single interim analysis for futility for the primary endpoint will be conducted after 79 deaths have been observed, using an O'Brien-Fleming stopping boundary. The Z-scale boundaries are 0.031, for the interim analysis, and 1.63 for the final analysis; these correspond to a p-value of 0.49 and HR of 1.59 for the interim analyses boundaries and a p-value of 0.052 and HR of 1.23 to reject non-inferiority (the alternative hypothesis).

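### Sample size, event count, timing and power do not fit together: at HR = 1, 400 patients give about 127 deaths (84% power) at month 82, not 166

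*Combined protocol and SAP*

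**What the plan says.** Section 10.2 takes exponential survival, 10 patients per month for 40 months, at least 42 months of follow-up and 400 eligible patients (420 accrued). Of control survival it says "The 3-year survival rate for SR (control group) appears to be approximately 80"%. The margin is HR 1.60 at a significance level of 0.05, and Section 10.3.1 makes the test one-sided. The closing summary of Section 10.2 claims: "if the true hazard ratio is 1, then there is a 90% probability of declaring non-inferiority". The trigger is: "the final analysis will occur after 166 deaths have been observed or about 82 months (6.8 years) after the first patient is enrolled".

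Section 10.3.2 says: "The interim analysis will take place after half the expected trial information (i.e. 79 deaths) has been observed". It gives a final boundary of Z = 1.63, corresponding to HR 1.23.

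On the length of survival follow-up the sections differ. Section 10.1.1 makes five years a floor for the primary endpoint. Section 7 says: "All patients will be followed for 5 years for survival and disease relapse/progression". Section 6 also gives five years, and the Study Calendar in Section 3 ends with yearly visits to year five.

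Section 1.4.1 says: "Target accrual for this study is 420 patients, with a projected accrual rate of 6-10 patients per month".

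**The concern.** Power is claimed at HR = 1, where both arms have the low control death rate, so deaths come slowly. A date worked out with SBRT deaths at the null rate is too early for that scenario. The trigger gives both a death count and a date, joined by a loose alternative, so a reader cannot tell which governs. If the date governs, the trial is analysed with too few deaths. If the count governs, the result comes about two years later than announced, and the sections that end follow-up at five years would prevent the count from being reached.

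The cost of lost power is specific here. Section 10.3.1 treats a confidence interval that includes 1.6 as evidence that SBRT is inferior. At 84% power, two truly equal treatments would produce that reading about 16% of the time instead of 10%.

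**Working it through.** **Inputs.** From Sections 10.2 and 10.3: one-sided alpha 0.05, margin 1.60, control 3-year survival 0.80, exponential survival, 40 months of accrual, 42 months of minimum follow-up, 400 eligible patients, 200 per arm. Assumed here: uniform entry and no loss to survival follow-up. Any loss lowers the counts.

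**1. Does the 90% reproduce from the number of deaths?** Required deaths = 4(1.645 + 1.282)² / (ln 1.6)² = 34.27 / 0.2209 = 155.1, so 156. Power at *d* deaths = Φ(ln 1.6 × √d / 2 − 1.645).
- 158 deaths: Φ(2.954 − 1.645) = 90.5%.
- 166 deaths: Φ(3.028 − 1.645) = 91.7%.

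The 90% is therefore correct if those deaths are observed.

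**2. Deaths at month 82.** The control hazard is λ = −ln(0.80)/36 = 0.006198 per month. The probability of death by month 82 is 1 − [exp(−42λ) − exp(−82λ)] / (40λ).
- Control rate: 1 − (0.77079 − 0.60153)/0.24794 = 0.3173.
- SBRT at HR 1.6 (hazard 0.009917): 1 − (0.65933 − 0.44342)/0.39670 = 0.4557.
- HR = 1: 400 × 0.3173 = 126.9 deaths.
- HR = 1.6: 200 × 0.3173 + 200 × 0.4557 = 154.6 deaths.

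| Patients | True HR | Deaths at month 82 | Power of the test at that count |
|---|---|---|---|
| 400 | 1 | 126.9 | 84.2% |
| 420 | 1 | 133.3 | 85.7% |
| 400 | 1.6 | 154.6 | 89.9% |
| 420 | 1.6 | 162.3 | 91.1% |

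Only the HR 1.6 rows come near the plan's figures. Simulating the futility look at 79 deaths leaves power at 84.0% to 84.4% for 127 deaths. To have 156 deaths at month 82 with HR = 1 would take 156 / 0.3173, about 492 patients.

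**3. When the target is reached without a five-year cap** (400 patients in 40 months; solve the expression in step 2 for the month).
- HR = 1: 158 deaths at month 101.5, 166 at month 106.9.
- HR = 1.6: 158 at month 83.8, 166 at month 88.1.
- HR = 1 with accrual at 6 per month: 158 deaths at about month 112 (420 patients over 70 months) to 116 (400 over 66.7 months).

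**4. If follow-up stops at 60 months per patient.** The probability of death is 1 − 0.80^(60/36) = 0.3106 at the control rate and 1 − 0.80^(1.6 × 60/36) = 0.4485 at HR 1.6. The most deaths that can ever be seen are:
- HR = 1: 124.2 (400 patients) or 130.4 (420).
- HR = 1.6: 151.8 (400) or 159.4 (420).

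All are below 166. At month 82 with this cap and HR = 1, 400 patients give 117.0 deaths and 81.5% power.

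**5. Which total?** 79 as half the information gives 2 × 79 = 158; half of 166 is 83. The HR at the final boundary is 1.6 × exp(−1.63 × 2/√d), which is 1.234 at 158 deaths and 1.242 at 166. The stated 1.23 fits 158. The interim HR of 1.59 does not help, since it comes to 1.589 with half of either total.

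**The case against.** The strongest reply is that power in a log-rank design follows the number of deaths. Section 10.2 names a count and gives month 82 only as approximate. If the analysis waits, power is at least 90% with no extra patients. This stands: the loss to 84% arises only if the calendar date is allowed to govern.

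A reader might also infer that 166 deaths can never occur. The documents do not support that as a general statement. Section 10.1.1, which defines the primary endpoint, makes five years a minimum, and on that reading 166 deaths are reachable, though late. Impossibility follows only if the fixed five years of Sections 6 and 7 and the Study Calendar is a ceiling. What stands is a conflict between sections that decides whether the target can be met.

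The 166 may not be a slip. 158 × 1.05 = 165.9, so it could be 158 inflated by the 5% over-accrual. That is an inference, since the plan does not say so. It would still leave the interim at 79 below half of the stated total.

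The accrual figures are a minor matter. 420 patients in 40 months need 10.5 per month against a projected 6 to 10, which means 42 to 70 months. Section 10.2 openly uses the top of that range and calls 40 months approximate.

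**Conclusion.** The concern holds as a mismatch between patient numbers, date, death count and power. At HR = 1, where the 90% is claimed, 400 patients at month 82 give about 127 deaths and 84% power (133 deaths and 86% if all 420 count). The stated date appears to have been computed with SBRT deaths at the null HR; the plan does not say which HR it used. At HR = 1 with continued follow-up, 158 to 166 deaths arrive about 20 to 25 months after month 82. With follow-up capped at five years, 166 is out of reach at HR = 1 and at HR = 1.6, even with 420 patients. The plan also carries two event totals, 158 and 166.

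It would go too far to conclude that the design lacks 90% power or that the trigger cannot be met. Each depends on one reading of an ambiguous text. These results rest on exponential survival at the plan's 80% control rate, uniform entry and no loss to survival follow-up.

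**What to change.** - **One event target throughout.** Either 158 deaths with the interim at 79, or 166 with the interim at 83 and recomputed boundaries. The first matches the stated final HR of 1.23 and gives 90.5% power.
- **Event-driven final analysis.** Remove the alternative date from the trigger. Reconcile Section 10.1.1 with Sections 6 and 7 and the Study Calendar, so that vital status is collected until the target is met. State the expected date at HR = 1: for 158 deaths, about month 102 with 400 patients accrued in 40 months, or about month 112 to 116 if accrual runs at 6 per month.
- **If month 82 is kept,** restate power at HR = 1 as about 84%, or about 82% if follow-up is capped at five years per patient.

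The cost is protocol wording plus either a later readout with a yearly vital-status check on survivors, or a less favourable stated power. No extra patients are needed.
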